## 1.5 NIHL in Police Officers

Both continuous and impulse-induced NIHL are sensorineural in nature. Unlike other injuries, sensorineural hearing loss will continue to progress with age (Kujawa and Liberman, 2006, 2009; Fausti et al., 2009). The incidence of hearing loss disability can increase four-fold after an average of only 4 years of active service among individuals with mild and moderate hearing loss prior to joining to the military (Gubata et al., 2013), suggesting NIHL from repeated noise exposure can cause more auditory damage in military service members with prior hearing loss. Similarly, police officers are repeatedly exposed to both continuous and impulse noises. A large population study of police officers (a total of 1880 subjects with 887 police officers) found that police officers were 1.4 times more likely to have a selective NIHL at 4 KHz than civil servants (Lesage et al., 2009). A subsequent study of 543 police officers found that of the officers identified with hearing loss, 93% presented with mild NIHL (26-40 dBA), 3.5% with moderate NIHL (41-60 dBA), and 3.5% with severe NIHL (61-80 dBA). Further analyses indicated a strong association of NIHL with age, duration of service and rank (Win et al., 2015). Several researchers have found NIHL across police populations. Lesage and colleagues (2009) found NIHL in 28% of police officers investigated, Shrestha and colleagues (2011) found NIHL in 66.4% of police personnel studied, and Gupta and colleagues (2015) found 22% of a police population presented with NIHL. Furthermore, tinnitus has been reported by several police officers across

studies (Singh & Mehta, 1999; Shrestha et al., 2011; Win et al., 2015; Thirugnanam et al., 2017). Based on this evidence, police officers are an ideal population for this project.

Hearing studies on police officers were performed by the current researchers in Northeast Ohio from 2017-2018 ([name] & Steiger, 2020). Hearing assessments were performed on 30 police officers, ranging from 35-61 years of age. 40% of these individuals served in the military, 26% of these individuals were part of the SWAT team, and 10% of the population served for both the military and the SWAT team at some point of their career. Results indicated that 73% of the officers presented with some degree of permanent hearing loss. Specifically, 70% of the population presented with evidence of NIHL, as characterized by a sensorineural hearing loss with the greatest amount of loss at 4-6 kHz, seen as a notch or dip on the audiogram (McBride & Williams, 2001). Initial signs of NIHL may present as a distinct notch from 3-6 kHz even in the presence of “normal hearing,” where thresholds fall at or above 25 dB HL, another observation observed from this study. Furthermore, evidence of NIHL was observed from absent otoacoustic emission recordings and absent high-frequency audiometric thresholds in the presence of normal audiometric results from .25-8 kHz. An increased sensitivity of OAEs in comparison to audiometric thresholds has been found whereby low-level OAEs indicate an increased risk of future hearing loss by as much as nine-fold (Marshall et al., 2009).

## **2.0 STUDY OBJECTIVES**

### **2.1 Primary Objective**

To determine if ZNS is more effective than placebo in preventing permanent threshold shift (PTS) in police officers identified with temporary threshold shift (TTS) following shooting range noise exposure.

### **2.2 Secondary Objectives**

To determine if ZNS is more effective than placebo in the prevention of additional auditory dysfunction in police officers following shooting range noise exposure as measured by ultra-high frequency audiometry, distortion product otoacoustic emissions (DPOAE), electrocochleography (EcochG) and words-in-noise (WIN) scores, and to determine a PGx link between NIHL and ZNS treatment effect.

## **3.0 ELIGIBILITY CRITERIA**

### **3.1a Screening Inclusion criteria**

1. Police officers who are scheduled for firearm training and/or certification on the range.
2. At least 18 years of age.
3. Air conduction thresholds are to be no worse than 25 dB HL from 0.5 kHz to 3 kHz, no worse than 30 dB HL at 4 kHz, and no worse than 45 dB HL at 6 and 8 kHz prior to shooting range exposure.

4. Observed air-bone gap < 10 dB HL at .5, 1, 2 and 4 kHz, with normal tympanometry.
5. Ability to understand and willingness to sign an IRB approved written informed consent document.

### **3.1b Enrollment Inclusion Criteria**

1. Observed audiometric TTS  $\geq$  10 dB HL at 2, 3, 4 and/or 6 kHz

### **3.2 Exclusion Criteria**

1. History of known sulfa allergy or hypersensitivity to carbonic anhydrase inhibitors.
2. History of moderate-to-severe kidney or liver disease.
3. Acute viral, bacterial, fungal or parasitic infection.
4. History of seizures.
5. Currently pregnant or breast-feeding.
6. Any current or history of otologic disorder.
7. History of ototoxic drug use.
8. Current use of strong/moderate 3A4 inhibitor/inducer and grapefruit juice.

Note: For secondary outcomes analysis only, exclusion criteria is as follows:

- a) DPOAE data will be used as a secondary outcome measure of TTS, and participants will be excluded if their DPOAE is absent at more than 4/10 frequencies. Criteria for a present response is any response that is  $> 5$  dB SPL above the noise floor and replicable within  $\pm 5$  dB SPL.
- b) ECochG: Participants will be excluded if the ECochG/ABR wave I response is absent.
- c) WIN test: Participants with WIN scores greater than moderate difficulty or 14.9 dB SNR will be excluded.

Participants will not be excluded from the study for not meeting secondary outcome criteria.

### **3.3 Inclusion of Women and Minorities**

Both men and women and members of all races and ethnic groups are eligible for this trial.

#### **4.0 STUDY DESIGN**

A randomized, double-blind, and placebo-controlled clinical trial has been designed.

Study participants will be recruited from the Akron Police Department, Summit County Police Department, and other local surrounding police departments. Police officers will be offered participation if they are training for firearm certification as part of their standard occupational requirements. These are officers that would be recommended and/or required to complete these trainings/certifications despite this investigation and this investigation will have no influence on audiologic recommendations.

The primary efficacy endpoint will be the proportion of PTS-positive subjects defined as the ratio of PTS-positive subjects to total number of subjects within each study arm/group. Subjects defined as PTS-positive will demonstrate an increase in threshold that is  $\geq 10$  dB HL at any frequency from 2-6 kHz post-shooting as compared to baseline audiogram.

The secondary efficacy outcome measures will be: (1) the proportion of PTS-positive subjects as defined above, but the definition of PTS will also include the NIOSH red flag guideline for permanent threshold shift: an increase in hearing threshold level of 15 dB or more at any frequency (2, 3, 4, 6 kHz). (2) The rate of temporary cochlear change as measured by a DPOAE amplitude shift at any frequency that is significantly greater than the stability of each measurement (i.e., 95% confidence interval of each measurement do not overlap). The rate of DPOAE shift is the ratio of DPOAE shift-positive subjects to total subjects within each arm.

Interested police officers will be consented and enrolled in the study. They will then undergo screening for TTS following shooting range noise exposure. Those officers identified with TTS will be randomized via an interactive randomization tool (IRT) and assigned to a study group. Once assigned the subject will be provided a kit that will contain either ZNS (100 mg PO) or a placebo. The ZNS and placebo capsules will look, taste, and smell the same. Participants will be instructed to take zonisamide without food. We will recommend that capsules be swallowed whole per the current approved labeling. Those without TTS will be finished with their study commitment.

The study will be “masked” or “blinded” in the sense that all the study participants and the study team members will be blinded to the assignment in the study groups. Only the pharmacist who will prepare the study drug kits and the unblinded statistician will have access to the kit assignments. The Medical Monitor will be contacted. A copy of the randomization list with study ID assignments will be saved in a limited access folder on a secure network server at Pharm-Olam. The Medical Monitor will

be contacted in emergent medical cases when knowing the treatments assignment is mandatory for clinical care of the study subject.

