**Electrocochleography (ECochG):** An ECochG is an electrophysiological measurement of the cochlea in response to sound. It is a clinically-approved auditory evoked potential that is used to evaluate the status of both the cochlea and the auditory nerve fiber. This measurement is obtained by inserting a soft gold-foiled earphone into the participant's ear. This earphone serves to deliver a series of clicks, as well as an electrode to measure the electrophysiological response of the cochlea to the sound. The electrode montage is completed with a ground electrode on the forehead at midline and a gold-foil electrode in the contralateral ear to serve as the inverting electrode. The impedance between electrodes will be  $< 3 \text{ k}\Omega$  for all participants. The click stimuli at 90 dB nHL used for the study will be repeated 2000 times so that the recording signal can be averaged with artifact rejection. The measurement will be repeated three times. Testing time will take 45 minutes to 1 hour.

**Distortion Product Otoacoustic Emissions (DPOAE):** DPOAEs are a measure of outer hair cell function and will be used as an indicator of changes in cochlear health and possible PTS in the early period following noise exposure. A soft earphone will be inserted into the participant's ear and a series of tones at a comfortable volume will be played at varying frequencies. No participation is required of the participant as DPOAE are an objective assessment of cochlear health. The measurement system (Interacoustics Titan DPOAE440) will record the level of the emissions evoked by two primary tones, f1 and f2 ( $f_2/f_1 = 1.22$ ) at levels 65 and 55 dB SPL respectively. The f2 primary tone will be swept from 1- 6 kHz, and will be repeated at least five times per session in order to calculate the stability of the emission at each session. All data will be identified and stored on a password protected computer. DPOAE recording will take about 20 minutes to complete.

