## 5.2 Randomization

Following identification of TTS, eligible participants will be randomized via an interactive randomization tool (IRT) in a balanced fashion into one of two study groups: ZNS (100 mg PO) or placebo. Randomization will be based on a randomization list generated from the study statistician using a computer algorithm written in SAS using randomly selected blocks of sizes 2. Within each block of 2, there will be 1 subject assigned to each study group. To balance noise-exposure history across study arms we will employ stratified randomization. The subjects will be stratified based on noise exposure survey responses (see table below), and will then be randomized to study groups. The random assignment of subjects to the different study groups will be associated with consecutively assigned study identification numbers (Study ID) which will be unique for each study participant. The stratified randomization kit list will be provided to Advanced Rx who will package and label the drug for shipment to the pharmacist for each participant. Each bottle will be labeled with the kit number, study ID, and instructions on how to take the medication. The bottle will not contain any information of the treatment allocation.

- ZNS (100 mg PO) group
- Placebo PO group

Name	Description
1: High Noise	Screening: LENS-Q Adapted for Police Officer

Name	Description
	
1A Or 2A Or 3A =
 
a.Daily, Or b.Less than daily/more than weekly, Or c.Weekly, Or d.Less than weekly/more than monthly Or e.Monthly
 
OR
 
1C Or 2C Or 4C <math>\geq 5</math> Years

2: Low Noise	
Screening: LENS-Q Adapted for Police Officer
 
1A AND 2A AND 3A =
 
f.Less than monthly/more than yearly, g.Yearly, h.Less than yearly Or i.Never
 
OR
 
1C AND 2C AND 4C <math>< 5</math> Years

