### **5.4 Follow-Up Assessments (Visits 3, 4 and 5)**

The follow-up assessments will occur after training and include the following tests or procedures:

1. Audiogram and DPOAEs to measure for TTS and auditory changes, as soon as possible after the training session. The exact time of testing following training operations will be documented. A clinical ear exam will be completed prior to the audiogram and DPOAEs. (follow-up visit 3 and 5).
2. Baseline environmental/ambient sound measurements will be recorded at the start of each test session, including the peak ambient noise level and the average noise level (follow-up visit 3 and 5).
3. Collection of blood for laboratory testing to include an electrolyte panel, BUN, Cr, ALT, and AST. This will occur within 12-24 hours following drug intake (follow-up visit 4).
4. Cognitive assessments within 24 hours following drug intake, including (follow-up visit 4):
  - a. Digit-symbol substitution test (processing speed)
  - b. Verbal fluency (working memory, speech/language)
  - c. Stroop (Executive function, inhibition)
  - d. List Learning task/RBANS (memory)

Additionally, after each officer is asked about potential study-related side effects for safety monitoring, they will be asked a question regarding their feeling of safety on the job, i.e. they will be asked *“if they feel safe partaking in required responsibilities associated with their job at this time or not?”*

5. Completion of LENS-Q 1-minute noise screening for noise exposure questionnaire (follow-up visit 5).
6. Audiogram, ECochG, DPOAE, and WIN testing 30 days (+/- 3 days) after each training session to assess for PTS and auditory changes, only if TTS is observed from #1 (visit 5).
7. Documentation of adverse events at all follow-up visits (5-30 minutes post, within 24 hours and at 30 day visit) (follow-up visit 3, 4 and 5).

Follow-up assessments will be planned at the stated time points; actual follow up times may vary due to patient logistics and compliance.

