## 9.0 STUDY CALENDAR

	VISIT 1 Screening Assessment	VISIT 2 Baseline Assessment	Post-training		
			VISIT 3 Within 5-30 Minutes	VISIT 4 Within 24 Hours	VISIT 5 30 days (+/- 3 days)***
Informed Consent	X				
Demographic Info	X				
Current Meds	X				
Questionnaires	X				X
Cognitive Assessment		X		X	
Clinical ear exam	X	X	X		X
Audiogram	X	X	X		X
ECochG		X			X
DPOAE		X	X		X
WIN		X			X
Sound Measurements	X	X	X		
Randomization			X*		
Oral Dose* ZNS or Placebo			X**		
Blood draw**		X		X	
AE Assessment			X	X	X

\* Dispensed after training if TTS is identified on audiogram 5-30 minutes after shooting.

\*\* Blood draw: Electrolyte panel, BUN, Cr, ALT, and AST; DNA analysis and serum pregnancy test at baseline

\*\*\* If TTS is seen from pure tones after each training session

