3.3 Secondary efficacy outcomes

The study is designed to test the null hypothesis associated with the primary efficacy measure. Nevertheless, it provides a great opportunity to evaluate the impact of ZNS on other audiometric and clinical measures:

- DPOAEs: Distortion product otoacoustic emissions will be measured at baseline

(before shooting), as well as within 5-10 minutes after shooting and 30 days (+/-3 days) post-shooting (for officers with positive TTS) to measure both temporary and permanent changes in DPOAE amplitude relative to baseline. A change is noted in DPOAE amplitude at any frequency that is significantly greater than the stability of each measurement (i.e., 95% confidence interval of each measurement do not overlap).

- Ultra-high frequency audiometry: Ultra-high frequency audiometry (10-14 kHz) will be measured at baseline (before shooting), 30 days (+/-3 days) after shooting (for officers with positive TTS) to measure for both temporary and permanent high frequency audiometric changes. A significant change is defined for any frequency that is greater than 5 dB HL from baseline thresholds.
- ECochG: Electrocochleography will be measured at baseline (before shooting) and 30 days (+/-3 days) after shooting (for officers with positive TTS) to measure for changes in ECochG AP amplitude, latency and width.
- WIN testing: The Words-In-Noise test will be administered at baseline (before shooting) and 30 days (+/-3 days) after shooting (for officers with positive TTS). The respective scores will be converted to Z-scores to evaluate for any change in scores relative to baseline.

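### Secondary outcome 2, the per-arm rate of temporary DPOAE shift, can only come from Visit 3, which falls before or close to dosing, so as worded it tells little or nothing about the drug

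*Protocol*

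**What the plan says.** Protocol 4.0 lists two secondary efficacy outcomes. The second is "The rate of temporary cochlear change as measured by a DPOAE amplitude shift at any frequency" that exceeds measurement variability. It is a binary outcome compared between groups: "The rate of DPOAE shift is the ratio of DPOAE shift-positive subjects to total subjects within each arm". No visit or time is attached to it. Protocol 3.2 gives the measure the same role: "DPOAE data will be used as a secondary outcome measure of TTS".

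For the early recording, Protocol 5.4 asks for "Audiogram and DPOAEs to measure for TTS and auditory changes, as soon as possible after the training session" and assigns it to Visit 3. On allocation, Protocol 5.2 says "Following identification of TTS, eligible participants will be randomized via an interactive randomization tool (IRT"). On the capsule, the calendar footnote in Protocol 9.0 reads "Dispensed after training if TTS is identified on audiogram 5-30 minutes after shooting"; SAP 2.5 and 2.6 agree.

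SAP 3.3 schedules DPOAE at baseline, "as well as within 5-10 minutes after shooting and 30 days (+/-3 days) post-shooting", to capture both transient and lasting change. It says when a change is counted but defines no per-arm rate. Protocol 12.2.2 and SAP 7.1.2 treat DPOAE as a continuous outcome analysed by ANCOVA, in a list tied to day 30, with no adjustment for multiple comparisons.

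**The concern.** An efficacy outcome has to be measured when the treatment could have affected it. Outcome 2 is labelled temporary, and the only session at which a temporary change can be seen is the one that also decides who is randomized and dosed. Comparing arms on a quantity already fixed at that point is a check of baseline balance, not of efficacy.

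The risk is misreading in either direction. A similar rate in the two arms could be reported as no cochlear protection, and a chance imbalance as protection. Meanwhile the recording that can address the secondary objective, at Visit 5, is not what outcome 2 describes.

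**Working it through.** **1. Where a temporary shift could be measured.** From the calendars (Protocol 9.0, SAP 2.6) and Protocol 5.4:

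| Visit | Timing | DPOAE | Relation to the single dose |
|---|---|---|---|
| 2 | Baseline | Yes | Before |
| 3 | 5-30 minutes after shooting | Yes | Before or close to it; order not stated |
| 4 | Within 24 hours | No (blood, cognition, adverse events) | After |
| 5 | Day 30 ± 3 | Yes | After |

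Visit 5 is where permanent shift is assessed, so a temporary-shift rate has only Visit 3 minus Visit 2 to draw on. The audiogram listed with the Visit 3 DPOAE must come before randomization and the capsule. Whether the DPOAE itself does is not written down.

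**2. Expected difference if the recording precedes the dose.** Let π be the probability of a shift at Visit 3. Randomization gives both arms the same π, and the drug has not been taken, so

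expected difference = π − π = 0, for any drug effect.

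**3. How large a chance difference could be.** The 95% range of the observed difference is about ±1.96 × √(2π(1−π)/n). With n = 66 per arm (Protocol 12.3) and assumed rates:
- π = 0.50: 1.96 × √(0.50/66) = 1.96 × 0.0870 = ±17 percentage points.
- π = 0.20 or 0.80: 1.96 × √(0.32/66) = 1.96 × 0.0696 = ±14 percentage points.

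**4. How often it would look significant.** Neither document names a test or alpha for the rate. As an assumption, take the primary's Fisher test at one-sided 0.025 with 66 per arm. Exact enumeration with the same rate in both arms gives:

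| Assumed common rate | Probability of rejection |
|---|---|
| 20% or 80% | 1.5% |
| 30% or 70% | 1.6% |
| 50% | 1.5% |
| 90% | 1.2% |

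This is type I error only; it does not rise with a better drug.

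**5. The plan's nearest figure.** No power is stated for the DPOAE rate. Protocol 12.3 states 96.1% for TTS as a secondary outcome: 63 per arm, 80% versus 48%, one-sided alpha 0.0235. With a pooled z test, the mean rate is 0.64, and

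power = Φ[(0.32 × √63 − 1.986 × √(2 × 0.64 × 0.36)) / √(0.80 × 0.20 + 0.48 × 0.52)]
= Φ[(2.540 − 1.348) / 0.640] = Φ(1.86) = 96.9%.

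Exact Fisher gives 95.5%, and the arcsine approximation with continuity correction 95.1%. The arithmetic is sound, but the premise is not available in this trial. Protocol 3.1b makes TTS a condition of enrollment, so among randomized officers the Visit 3 rate is 100% in both arms by construction, not 80% against 48%. Protocol 12.2.2 and SAP 7.1.2 also name audiometric TTS as an outcome while using average post-shooting TTS as a covariate.

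**6. Early timing.** SAP 3.3 puts the early DPOAE at 5-10 minutes after shooting; both calendars give 5-30 minutes. Protocol 5.1 says "DPOAE recording will take about 20 minutes to complete". These statements need to be reconciled.

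**The case against.** The strongest reply is that outcome 2 is undated and the analysis sections already contain a sound DPOAE comparison. That is right as far as it goes: the day-30 ANCOVA is post-dose and can show an effect. A reader might infer that the trial's DPOAE data cannot show any effect of zonisamide; the documents do not support that. What remains is that the day-30 ANCOVA is continuous and concerns persistent change, whereas Protocol 4.0 names a binary rate of temporary change.

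A reader might also expect a rate table to be produced and read as efficacy. The SAP table index (12.1) lists only DPOAE amplitude and noise floor, as actual values and change from baseline, and no test is specified for the rate. The rejection probabilities above therefore illustrate a comparison that Protocol 4.0 implies but the SAP does not plan.

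Nor do the documents fix an upper limit on drug exposure before the Visit 3 DPOAE. Subtracting 5 from 30 gives 25 minutes, but Protocol 5.4 lets actual times vary, and Protocol 12.4 and SAP 4.4 speak of screening within an hour of shooting. Similarly, a 20-minute recording is incompatible with a 5-10 minute window only if the window refers to completion rather than start.

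Finally, temporary could mean shifted at Visit 3 and recovered by Visit 5, which the drug could influence. Protocol 4.0 does not say this, and under that definition a protective drug could raise the rate by increasing recovery.

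**Conclusion.** The point holds in a limited form. The only recording that fits outcome 2 as worded is made before or close to dosing. If before, the true arm difference is zero and the result supports neither efficacy nor its absence; under the assumed test, significance would be a 1.2% to 1.6% chance event. If some recordings follow the dose, the difference need not be exactly zero, but it would depend on an order and an interval that the plan does not set.

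This rests on reading temporary as a shift seen at Visit 3, on the scheduled visits, and, for the percentages, on a borrowed test and assumed shift rates. The primary endpoint, its sample size and the day-30 DPOAE ANCOVA are not affected. The change is worth making because a named efficacy outcome should be able to respond to treatment.

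**What to change.** - In Protocol 4.0 and SAP 3.3, define outcome 2 as the proportion with a DPOAE shift at Visit 5 (30 ± 3 days) versus Visit 2.
- Report the Visit 3 DPOAE as a descriptive measure of initial injury, not as an efficacy comparison. Use it as a covariate in the Visit 5 DPOAE model only where it was recorded before the dose.
- Record the times of the DPOAE and of the dose so that their order is known. Protocol 5.4 already asks for the exact time of post-training testing. This is a recording requirement and does not say when the capsule should be taken.
- Reconcile the early DPOAE window in SAP 3.3 with the Visit 3 window in the two calendars.
- Reconcile Protocol 3.2, 12.2.2 and 12.3 and SAP 7.1.2, which treat TTS or early shift as an outcome, with Protocol 3.1b, where TTS is the entry criterion.

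The cost is wording and time entries; no test or visit is added. The downside is that the trial gives up its claim to test a drug effect on temporary cochlear change.

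### The DPOAE shift rule compares sessions using within-session intervals, at any frequency and in either direction, so its false-positive rate is uncontrolled

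*Protocol*

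**What the plan says.** Protocol 4.0 lists two secondary efficacy outcome measures. The second is a rate of temporary cochlear change judged from DPOAE amplitude, and an officer counts as positive on a "shift at any frequency that is significantly greater than the stability of each measurement (i.e., 95% confidence interval of each measurement do not overlap". This makes the result binary per officer: "The rate of DPOAE shift is the ratio of DPOAE shift-positive subjects to total subjects within each arm". SAP 3.3 carries the same rule: "A change is noted in DPOAE amplitude at any frequency that is significantly greater than the stability of each measurement".

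Protocol 5.1 says where the intervals come from. The sweep "will be repeated at least five times per session in order to calculate the stability of the emission at each session". Visit 2 (baseline), Visit 3 (after shooting) and Visit 5 (30 days) are separate sessions, and the probe is inserted at each.

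Protocol 3.2 implies 10 frequencies per recording: "participants will be excluded if their DPOAE is absent at more than 4/10 frequencies". It also gives the only repeatability figure in either document, a tolerance of 5 dB SPL either way, as part of deciding whether a response is present.

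Neither document gives:
- a DPOAE SD, within or between sessions;
- a minimum change or a direction;
- the ears to be scored;
- whether the interval is for a mean or for a single measurement.

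Protocol 12.2.2 and SAP 7.1.2 analyze DPOAE as a continuous variable by ANCOVA with baseline as a covariate. The table index in SAP 12.1 lists DPOAE amplitude and noise floor, but no table for the shift rate.

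**The concern.** An interval built from sweeps within one session measures sweep-to-sweep noise only. Refitting the probe and day-to-day variation move the session mean, and the interval does not contain that movement. Two sessions can therefore separate with no change in the cochlea.

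Two features add to this. Any one of 10 frequencies, in one or two ears, makes the officer positive. The words used for the change carry no sign, so a larger emission counts the same as a smaller one.

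The sweep count has a minimum but no maximum. If the interval is for the mean, more sweeps narrow it and make a positive result easier to reach.

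At stake is a named secondary efficacy outcome. A high background rate in both arms would shrink the difference between them and could be read as widespread cochlear change.

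**Working it through.** The documents state no rate, SD or power for this outcome, so there is no plan figure to reproduce. As a check on the power method used below, exact one-sided Fisher enumeration for the primary outcome (66 per group, 50% vs 25%, one-sided 0.025) gives 81.3%, against the stated 80.5%.

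**Inputs from the documents.** Five sweeps per session (the stated minimum), 10 frequencies, non-overlap of 95% intervals, 66 officers per group.

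**Assumptions.** Within-session SD of one sweep 1 dB. Session-change SD *b* (movement of the session mean between visits, apart from sweep noise) from 0 to 2 dB. No true change. One ear (10 comparisons) or two (20). Frequencies independent unless stated.

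**Step 1: the separation needed.** With a t interval for the mean, the half-width is t(0.975, 4)/√5 = 2.776/2.236 = 1.24 dB. Two such intervals separate at about 2 × 1.24 = 2.5 dB. With intervals for a single measurement, separation needs 2 × 1.96 = 3.9 dB or 2 × 2.776 = 5.6 dB.

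**Step 2: officers with no true change called positive.** Simulation, 20,000 officers per cell, CI of the mean. With independent comparisons the one-ear rate is 1 − √(1 − two-ear rate), for example 1 − √0.20 = 55%.

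| Session-change SD | One ear | Two ears |
|---|---|---|
| 0 dB | 5% | 10% |
| 0.5 dB | 16% | 30% |
| 1 dB | 55% | 80% |
| 1.5 dB | 86% | 98% |

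At 2 dB with two ears it is 99.9%. Correlation of 0.5 across frequencies lowers the 1 dB figures to 49% and 71%.

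**Step 3: the other reading of the interval.** At 1 dB with two ears, an interval for a single measurement gives 23% (1.96 × SD) or 4% (t × SD), against 80% for the CI of the mean.

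**Step 4: number of sweeps.** For the CI of the mean, the separation needed falls from 2.5 within-session SDs at 5 sweeps to 1.4 at 10 and 0.9 at 20. At *b* = 0.5 dB with two ears, the false-positive rate rises from 30% to 64% to 93%. With single-measurement intervals it does not rise: it is 3% or less at 5 sweeps and about 0 at 20.

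**Step 5: effect on the arm comparison.** If a share *f* of officers without a true change is called positive in both arms, the observed rate is *f* + (1 − *f*)*p*. At *f* = 0.5, a true 50% vs 25% becomes 75% vs 62.5%. No DPOAE effect size is given, so the two effects below are borrowed from the plan's PTS and TTS assumptions. Fisher power at 66 per group:

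| *f* | 50% vs 25% | 80% vs 48% |
|---|---|---|
| 0 | 81% | 97% |
| 0.3 | 45% | 81% |
| 0.5 | 28% | 60% |
| 0.7 | 14% | 33% |
| 0.9 | 3% | 4% |

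**Step 6: a directed rule with a 5 dB minimum.** The SD of the observed change is √(*b*² + 2/5).
- *b* = 1.5: SD 1.63 dB, P(decrease > 5 dB) = 0.0011 per comparison; over 20 comparisons, 1 − (1 − 0.0011)^20 ≈ 2%.
- *b* = 2: SD 2.10 dB, P = 0.0086; 1 − (1 − 0.0086)^20 ≈ 16%.

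**The case against.** The strongest reply is that the size is not in the documents. The SDs are assumed, the number of ears is not stated, and the wording can be read as an interval for a single measurement, which brings the 1 dB figure from 80% down to 23% or 4%. This stands. A reader might infer that most officers without a true change would be positive; the documents do not establish that, and the results run from under 5% to nearly 100%.

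A reader might also infer that the outcome cannot separate the arms. Misclassification equal in both arms dilutes the comparison: at *f* = 0.3 a true 80% vs 48% keeps 81% power, and loss is near total only at about 90%. Moreover, the specified ANCOVA of DPOAE amplitude does not use the rule at all.

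A third tempting reading is that the rule contradicts Protocol 3.2, where a response must be "dB SPL above the noise floor and replicable within" 5 dB either way. That tolerance helps decide whether a response is present. It is not a limit for change between visits, and the 2.5 dB separation depends on an assumed SD and a chosen interval. There is no contradiction.

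Finally, every randomized officer already has an audiometric TTS, so the analyzed officers are not untouched by noise. That is true, but an officer can still have no lasting DPOAE change at Visit 5, and the rule does not protect that officer from being called positive.

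None of this supplies the missing terms. Whichever interval is meant, session-to-session variation is outside it and increases count.

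**Conclusion.** The concern holds as a fault in the stated rule. Followed literally, it counts session-to-session variation and increases in emission as cochlear change, and nothing in either document limits how often that happens.

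The size is conditional. It rests on a within-session SD of 1 dB, five sweeps and independent frequencies. With a CI of the mean, false positives pass one half at a session-change SD of about 1 dB; with single-measurement intervals they are well below that at 1 dB. The dependence on sweep count applies only to the CI-of-the-mean reading.

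The consequence is a weaker comparison of shift rates. It does not reach the primary outcome or the continuous DPOAE analysis.

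**What to change.** In Protocol 4.0 and SAP 3.3:

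1. Count only decreases in amplitude from Visit 2.
2. Use a fixed five sweeps per session for the derivation.
3. In addition to non-overlap, require a decrease larger than a pre-specified test-retest limit. A provisional limit is 5 dB, borrowed from the response-presence tolerance in Protocol 3.2. With two ears and a CI of the mean it gives about 2% false positives at a session-change SD of 1.5 dB and 16% at 2 dB. Replace it if the sponsor has between-session data.
4. State whether the interval is for the mean or for a single measurement, and which ears count.
5. Score the between-arm comparison at Visit 5. Visit 3 DPOAEs belong to the post-shooting assessment that precedes dosing, so a comparison there could not show a treatment effect under any threshold.

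The cost is wording in two sections and one derivation. True decreases below the limit no longer count as a shift, and that loss of sensitivity has not been quantified; they remain in the planned ANCOVA.
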